## 6. STUDY DESIGN AND DURATION

### 6.1. Summary of Design

Those subjects meeting inclusion/exclusion (I/E) criteria will receive, on one day, a single C-raclopride and a single C-DTBZ PET brain scan to provide baseline measurement, along with a 3T MRI scan for PET co-registration. On a later date each subject will receive a single 3.0 g oral dose of Xyrem® followed by three scans: two C-raclopride scans at approximately one and seven hours and one C-DTBZ scan approximately five hours following Xyrem® administration. Subjects will participate in a final follow-up telephone call the day after taking Xyrem® for a brief interview.

The pilot study design required subjects to be scanned four times (e.g., baseline; one, 6 and 24 hours post- Xyrem®) with raclopride and four times with DTBZ, which would require one group of subjects receiving four raclopride scans, and a separate group of subjects receiving four DTBZ scans—for which cost would be high in terms of monies, number of subjects, and radiation exposure to humans. Further, subjects receiving raclopride scans would not be those receiving DTBZ scans and, importantly, it would not be possible to correlate in individual subjects the extent of dopamine buildup inside the dopamine neurone (with C-DTBZ) with the extent of dopamine released by the neurone (with C-raclopride).

We, and the external reviewers of our pilot data, feel that there is value in an approach that: 1) "measures" both intraneuronal (DTBZ) and extraneuronal (raclopride) dopamine in the same group of patients in order to assess presynaptic dopamine buildup as well as dopamine release; and 2) is cost effective in terms of number of scans and subjects. We will therefore follow a five scan approach: two baseline scans using both C-raclopride and C-DTBZ. On a separate day subjects will receive three scans after ingesting Xyrem®: C-raclopride at approximately one and seven hours post; C-DTBZ at approximately 5 hours post-Xyrem®.

The raclopride scan at one hour post- Xyrem® corresponds to the time we found the single dose of Xyrem® to be maximally sedating and for which we anticipate the maximal reduction of dopamine release. Based on our feasibility data, at five hours post-Xyrem®, dopamine should have been "well" accumulated within dopamine neurones and can be assessed by a DTBZ scan. The seven hour C-raclopride scan is conducted during drug withdrawal (approximately 14 Xyrem® half-lives) and would

correspond to the time a subject participates in morning work duties following the typical second night-time Xyrem® dose. This subject therefore might benefit from modest dopamine hyperactivity. Thus, this scan time has been selected for both “clinical” relevance and for logistical considerations.

## 6.2. Duration

The **study duration** for each subject will involve approximately one-two days medical screening, two PET/MRI scan days (baseline and Xyrem® day), including one MRI session for co-registration of the PET scans, and a follow-up telephone call the day after taking Xyrem®. Unscheduled visits may occur if required (e.g. subject must return for: blood work/EKG if could not be scheduled on same day as screening visit, etc.). Subject participation will likely occur over a period not longer than 5 weeks. Anticipated study start and finishing dates are September 1, 2015 and May 1, 2019, respectively.

## 6.3. Details of Study Design

### 6.3.1. Recruitment

Control subjects will be recruited by print and online advertisement and invited to contact the Research Coordinator (RC – by phone or email), who will explain the study and answer questions posed. If narcolepsy patient groups are available, the PI will speak to such groups, describe the study, and provide flyers/brochures explaining the study which will include a contact number for the RC. If the subject is interested, RC will proceed with a telephone/email screen, asking general questions to try to determine whether the subject will meet I/E criteria. If subject passes this screen they will be asked to come in for the screening and baseline evaluation day with RC.

In addition, patients meeting criteria for a diagnosis of narcolepsy with cataplexy may be referred by a specialist at sleep/neurology clinics aware of the study. The patients will be informed (through conversation and using the provided flyer/brochure) that there is an opportunity to participate in a PET study looking at the effects of a drug used to treat narcolepsy (Xyrem®) on brain dopamine. All patients will be informed that their potential participation or refusal will not jeopardize their care or change their clinical management. The patient can then contact the RC for further information if interested, and proceed through telephone/email screen for eligibility.

### 6.3.2. Schedule of Activities

Activity	Screening Visit(s)	Baseline Scan Day	Xyrem® Scan Day	Follow-up call
Written Informed consent	RC			
Consent review		RC	RC	RC/PI
Demographics/Drug - Alcohol Use History	RC			
Psychiatric Interview	RC			
Routine Blood Work  & EKG	CL			
Urine collection/drug screen 	RC	RC	RC	
Medical History & Physical Exam	SP			
I/E determination	PI/QI			
Adverse Event review/log		RC/PI/QI	RC/PI/QI	RC/PI/QI
MRI Scan		RIC-MRI		
I.V. or catheter placement		RIC-PET	RIC-PET	
Record/monitor vitals			A/QI	
PET Scans		RIC-PET	RIC-PET	
Xyrem® administration			A/QI	
Blood draw for GHB level			RIC-PET	
Interview regarding lingering effects of Xyrem®				RC/PI

Routine Blood Work (at screening) includes serum chemistry (sodium, potassium, chloride, urea (BUN), creatinine, total protein, albumin, total bilirubin, ALT, AST, ALP, GGT, LDH, calcium, magnesium, TSH, free T4), random glucose, CBC + differential, ESR,

PT/INR, and serum  $\beta$ -HCG for all women of childbearing potential. Urine drug screen includes a rapid response urine test panel immediately read by RC and broad spectrum analysis done by CAMH Clinical Lab. A = Anesthesiologist, CL = Clinical Lab, PI = Principal Investigator, QI = Qualified Investigator, RC = Research Coordinator, RIC-MRI = Research Imaging Centre MRI group, RIC-PET = Research Imaging Centre PET group, SP = Study Physician.

### 6.3.3. Pre-Study Screening and Baseline Evaluation (Days 1 and 2)

Subjects will come to CAMH for a Screening day visit, during which they will meet with RC who, after further explanation of the study, will take informed consent. Each potentially eligible person who has signed informed consent will be assigned a Subject ID in consecutive order starting from Jazz-001. Should the subject meet all criteria and continue through the study, they shall keep the same ID throughout. For those subjects who signed consent and subsequently fail to meet eligibility requirements, a minimal data set will be maintained under their Subject ID (i.e. consent form, demographics, assessments used to determine eligibility).

The following procedures will be performed at the screening visit(s):

- Obtain written informed consent
- Structured clinical interview for demographics, drug use history (including alcohol and nicotine using AUDIT questionnaire and Fagerstrom Test)
- Psychiatric interview for DSM-IV (DSM-5) Axis I disorders using SCID-NP, SIGH-SAD (Ham-D)
- Urine specimen collection for:
  - o Rapid Response urine test panel (results immediately assessed by RC)
  - o Broad spectrum urine drug analysis (assessed by CAMH Clinical Lab)
- EKG with 12-lead electrocardiogram (assessed by cardiologist)
- Blood collection for:
  - o Routine blood work (see schedule of events for detailed list)
  - o For female subjects of childbearing age, serum pregnancy test ( $\beta$ -HCG)
- Medical history and physical exam with study physician
- For narcolepsy subjects, if consent is given, a member of the study team will collect required information from the subject's referring physician in order to characterize their condition.

This visit will take approximately four hours, and may be broken up over more than one day in order for the physician to have access to the lab results prior to performing the physical evaluation.

The study physician will review all lab results once they are available, and make a recommendation for suitability for the study. If permission given, the study physician may contact the subject's family physician and/or review their medical records for corollary information to help alleviate any concerns regarding medical history or lab results if necessary. All the above information is provided to the QI and PI for final eligibility determination. If the subject qualifies and is enrolled in the study, the QI will provide a prescription for 3.0 g Xyrem®. RC will give the prescription to CAMH Pharmacy at least one week prior to the subject's scheduled Xyrem® scan day.

Subjects will be informed of their status, and if they are to continue in the study, RC will schedule the *Baseline Scan Day* appointment prior to subject leaving the screening visit (if possible).

Subjects will be informed that transportation to and from CAMH for all subsequent visits will be provided for them (i.e., by taxi) as required.

### 6.3.4. Treatment/Assessment visits

#### 6.3.4.1. Day 3: Baseline PET/MRI

During this visit the following tasks will occur:

- RC meets with the subject, reviews the tasks to be completed for the day, and confirms the subject is willing to continue
- Urine specimen collected for:
  - o Rapid Response urine test panel (immediately assessed by RC, must be negative for contraindicated drugs)
  - o Broad spectrum urine drug screen (assessed by CAMH Clinical Lab)
  - o Pregnancy test in females of child bearing age (immediately assessed by RC, must be negative)
- Subject receives a 3T MRI scan for PET co-registration (see below for details)
- A single I.V. line or fine needle catheter (one per tracer) is placed in the subject's arm for tracer administration
- Subject receives a single C-raclopride scan followed by a single C-DTBZ PET scan at CAMH PET Centre (see below for details)
- RC enquires about any adverse events (AEs) that the subject may have suffered as a result of the days activities; these are recorded on the AE log
- Subject is dismissed upon completion of 2nd scan

This visit should take approximately seven hours. While in the PET Centre, subjects will be provided with a private room where they can rest/lay down/sleep between procedures as necessary.

#### 6.3.4.2. Day 4: Xyrem® Administration Day

The Xyrem® scan day should take place within one week of the Baseline scan day.

During this visit the following tasks will occur:

- RC meets with the subject, reviews the tasks to be completed for the day, and confirms the subject is willing to continue
- RC enquires about any AEs since last visit; these are recorded on AE log
- Subject is interviewed by RC and by anesthesiologist re: physical status and recent use of any medication, food, or liquids. Subject must confirm no food (including milkshakes, smoothies or instant breakfast drinks) since previous night and no liquids for the past 2 hours. If this is not the case, subject does not take Xyrem®
- Urine specimen collection for:
  - o Rapid Response urine test panel (immediately assessed by RC, must be negative for contraindicated drugs)
  - o Broad spectrum urine drug screen (assessed by CAMH Clinical Lab)
  - o Pregnancy test in females of child bearing age (immediately assessed by RC, must be negative)
- An I.V. line is placed in the subject's arm to allow for blood sampling and tracer injection
- Subject is connected to a physiological monitor (supplied by PET Centre): vitals (HR, BP, Respiration rate, O2 saturation) are taken and recorded. Vitals must be within normal range (assessed by anesthesiologist) for subject to receive Xyrem®.
- A sample of venous blood (approximately 7 ml) is taken for baseline GHB measurement.
- 3.0 g liquid Xyrem® is prepared in CAMH Pharmacy, with sign-off by Pharmacist(s), RC and a 2nd member of study staff, confirming correct dosage. Each dosing cup will be labeled, sealed, and brought by Pharmacist together with RC or 2nd staff to PET scan room.

- Anesthesiologist confirms/signs that the drug has been delivered, the seal is intact, and the subject ingests the full dose; RC records the time dose was ingested.
- A sample of venous blood is taken approximately 0.5, 1, 3, 5 and 7 hours post-Xyrem® ingestion for GHB measurement
- Subject receives two C-raclopride scans starting approximately one and 7 hours post-Xyrem® and one C-DTBZ PET scan approximately five hours post-Xyrem®
- Anesthesiologist will monitor subject and record the time when level of consciousness and vital signs have returned to normal, indicating that it is safe for subject to leave any time after that point. RC will record the time that subject actually leaves the PET/MRI Centre (after the 7 hour PET scan); by taxi or with companion who will drive them home. Both RC and Anesthesiologist will sign-off on this discharge form.
- RC enquires about any AEs that the subject may have suffered as a result of the days activities
- After final scan and AE evaluation, subject is paid the honorarium for full completion of the study, reminded that he/she cannot drive or operate heavy machinery (including farm equipment), and should not engage in strenuous activities, consume alcohol or any sedatives, make important decisions or engage in any activity requiring mental alertness for the next 24 hours.
- Subject will be given a wallet card printed with study details (e.g., Xyrem® dose, date and time taken, precautions/warnings, contact information for study personnel) and told that this should be kept on them (in their wallet) as a reminder of the precautions necessary and also to provide emergency contact information
- Subject is then discharged

This visit will take approximately 10 hours.

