### 5.3. Inclusion Criteria

#### General inclusion

- Able to sign and date informed consent
- Willing and able to complete trial as described in protocol
- Age 19 or over, both genders
- Willing to forgo alcohol and any other sedative-hypnotic drug 48 hours prior to and 24 hours after Xyrem® administration

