## **9. CONCOMITANT MEDICATION**

Subjects will be carefully screened at the beginning of the study to ensure that they are healthy and safely able to take Xyrem®. If subjects are currently on medication (including antidepressants for cataplexy) to treat a medical or mental illness, this condition must be stable/controlled, and they must be on a stable dose of said medication. The QI will determine whether the subjects' medications would be contraindicated. On the Xyrem® Scan day, specifically disallowed drugs/medications are any sedative-hypnotics, or any other CNS depressants including alcohol.

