### **13. STATISTICAL ANALYSIS**

The Biostatistical Consulting Service at CAMH, who provided the power calculations, will continue to advise on all statistical analyses to be conducted. Prior to analysis, data will be screened to ensure that underlying assumptions for statistical procedures are met. Should any demographic characteristic be found to be associated with outcome measures, they will be included as covariates in subsequent analyses. Changes in raclopride binding in whole striatum will be tested using a mixed model, with raclopride binding the dependent variable and time (baseline vs. one hour post-Xyrem® and vs. 7 hours post- Xyrem®) as the categorical independent variable. An unstructured covariance structure will be assumed. Should a significant time effect be detected, a series of Bonferroni-adjusted pairwise comparisons will be carried out. Changes in DTBZ will be assessed using a paired t-test. Subcompartments of striatum will be examined in a separate exploratory analysis. An exploratory correlation (Pearson) will investigate relationship between DTBZ binding changes at five hours (dopamine buildup) vs. raclopride changes at 7 hours (release of dopamine that had been "built-up").

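### Food, liquid and alcohol conditions are set for the Xyrem day but not for the baseline scan day, and matched scan start times are not required, so any systematic day difference is mixed with the drug effect

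*Combined protocol and SAP*

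**What the plan says.** **Xyrem day.** Section 6.3.4.2 states: "Subject must confirm no food (including milkshakes, smoothies or instant breakfast drinks) since previous night and no liquids for the past 2 hours". A subject who fails this check is not dosed; no other consequence is given.

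**Alcohol.** The general inclusion criteria (section 5.3) count abstinence from dosing: "Willing to forgo alcohol and any other sedative-hypnotic drug 48 hours prior to and 24 hours after Xyrem® administration". Section 9 names one day: "On the Xyrem® Scan day, specifically disallowed drugs/medications are any sedative-hypnotics, or any other CNS depressants including alcohol".

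**Baseline day.** Section 6.3.4.1 lists urine tests, the MRI, then one raclopride scan followed by one DTBZ scan. It gives no food, liquid or alcohol condition and no start times. On length it says: "This visit should take approximately seven hours".

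**Order and gap.** Baseline comes first. For the second day: "The Xyrem® scan day should take place within one week of the Baseline scan day". Raclopride is scanned at about 1 h and 7 h after the dose and DTBZ at about 5 h; "This visit will take approximately 10 hours". Patients and controls are all dosed (sections 5.1 and 6.1).

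**Analysis (section 13).** Raclopride in whole striatum goes into a mixed model with time as the only named factor, then: "Should a significant time effect be detected, a series of Bonferroni-adjusted pairwise comparisons will be carried out". For the other tracer: "Changes in DTBZ will be assessed using a paired t-test". Scan day and time are recorded on the CRF (section 14), but no planned analysis uses them.

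**The concern.** The trial asks whether a single dose causes a change in binding, and it answers by comparing each subject with his or her own baseline. That comparison isolates the drug only if the two days are otherwise alike. Here the protocol imposes pre-scan conditions on one side of the contrast and not on the other. Because day order is fixed and no one is scanned twice without the drug, the data cannot show afterwards whether a mean difference came from the drug or from the day. The control group does not help with this, since controls take the drug in the same order.

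DTBZ is the most exposed outcome: one baseline scan, one post-dose scan and no same-day comparator. The 7 h raclopride contrast is next, because it rests on the smallest pilot effect at the planned times. The estimated size of every change is also affected.

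**Working it through.** **1. How far the dosing-linked alcohol rule reaches back.** Taking the two days at similar clock times, the hours of the 48 h before baseline that the rule covers are max(0, 48 − 24 × gap in days). A gap of 1 day gives 24 h; a gap of 2 to 7 days gives 0 h.

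**2. The plan's own power figure.** Section 5.1 states power above 80% at alpha 0.05 with 15 subjects for changes of pilot size. It prints no SD, so the figure cannot be reproduced. It can be inverted with a paired t-test (noncentral t, 14 df, two-sided). The pilot raclopride means (section 2, two subjects, 4.5 g) are (6 + 13)/2 = +9.5% at 45 min and (−7 − 6)/2 = −6.5% at 6 h. For 80% power at n = 15 the standardised change must be 0.778 at alpha 0.05, or 0.876 at alpha 0.025 (Bonferroni for two comparisons). For −6.5% the SD of change can then be at most 6.5/0.778 = 8.35 points, or 6.5/0.876 = 7.42 points. I use SDs of 5 and 8 points as assumptions; 8 is near the upper end.

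**3. Uniform day shift, no drug effect, DTBZ test at alpha 0.05.** Noncentrality = shift/SD × √15; critical value 2.145.

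| Assumed shift (points) | SD 5: noncentrality | Significant | SD 8: noncentrality | Significant |
|---|---|---|---|---|
| 0 | 0 | 5% | 0 | 5% |
| 1 | 0.775 | 11% | 0.484 | 7% |
| 2 | 1.549 | 30% | 0.968 | 15% |
| 3 | 2.324 | 58% | 1.452 | 27% |

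**4. The 7 h raclopride contrast** (per comparison at alpha 0.025, critical value 2.510, before the overall time test).
- *Hiding a true fall.* True change −6.5 with an opposing 3-point shift leaves −3.5. Power goes from 99% to 59% (SD 5) or from 73% to 24% (SD 8).
- *Creating a false fall.* Suppose a real 1 h rise of 9.5, no 7 h effect and a shift of −3. The expected contrasts are 9.5 − 3 = +6.5 at 1 h and 0 − 3 = −3 at 7 h. The 7 h contrast is then significant in 45% (SD 5) or 18% (SD 8) of trials.

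**5. If conditions merely vary at random between subjects.** The SD becomes √(SD² + s²). With s = 3, 5 becomes 5.83 and 8 becomes 8.54. Power for −6.5% at 7 h goes from 99% to 95%, or from 73% to 67%.

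**6. A DTBZ effect of pilot size.** For a true −14% (pilot, 6 h) and an opposing 3-point shift, power stays above 99% at both SDs. At half that effect (−7%), it falls from 99.9% to 82% (SD 5) or from 88% to 44% (SD 8). The smaller effect is worth showing because the pilot used 4.5 g and this study uses 3.0 g (section 8.2).

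**7. Does matching fit the baseline visit?** The 1 h and 5 h scans start 4 h apart. Four hours plus a scan of about 60 minutes is 5 h of the planned 7 h. The MRI (up to about 1 h, section 6.4) fits before the first scan or in the 4 − 1 = 3 h gap.

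**The case against.** The strongest reply is that nothing in the documents says a meal, a drink or the time of day changes raclopride or DTBZ binding. That stands: the shift and the SD above are both assumed. An absent rule by itself leaves intake free to vary between subjects, which is nearer to step 5 than to step 3, and the loss there is small. The 58% needs the same 3-point shift in every subject.

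Several controls do reach the baseline day. Section 5.4 excludes sedatives and dopamine-modulating medication at the start of the baseline period, and substance abuse within the past year. The urine checks are the same on both days. Section 11 allows a subject's participation to end for a condition that would confound the PET outcome. Section 5.3 also words alcohol as one of the sedative-hypnotics, so the section 5.4 exclusion might be read to cover it, though that list is mainly of medications and the baseline period is not defined. None of these sets a food, liquid or clock-time condition.

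The food difference is clearest for the 1 h scan. The documents do not say whether subjects eat later in the visit, so fasting state at 5 h and 7 h is unknown. Consent pages are not in the file and may hold pre-scan instructions; the point concerns the protocol text only.

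A reader might infer that the baseline scans will be run at different clock times. The text does not show that. It does not require matching, and it keeps the order of raclopride then DTBZ on both days.

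A reader might also infer that the predicted rise-then-fall in raclopride is safe, because a constant offset alone cannot give opposite signs at 1 h and 7 h. Step 4 shows why this goes too far: combined with a real 1 h rise, an offset can produce a false 7 h fall or hide a true one.

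**Conclusion.** The point holds as a gap in design control. The plan sets pre-scan conditions on the Xyrem day and not at baseline, and no planned analysis can separate a systematic day difference from the drug effect in the DTBZ test or in any raclopride contrast with baseline. It would be a stronger claim to say that the results will be biased, and the documents do not support that: they give neither the existence, direction nor size of a shift.

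The possible size runs from negligible (random variation only, or a DTBZ effect as large as in the pilot) to material (a uniform shift of 2 to 3 points, particularly for a small DTBZ change or the 7 h raclopride contrast). These figures rest on n = 15, an assumed SD of change of 5 or 8 points, and a paired t approximation to the mixed model. I rate it a cheap improvement of minor to moderate severity.

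**What to change.** 1. In section 6.3.4.1, apply the same pre-scan food, liquid and alcohol conditions that the Xyrem day carries. Confirm and record them at both visits, and keep intake during the visit comparable.
2. Set target start windows so that baseline raclopride matches the clock time of the 1 h scan and baseline DTBZ that of the 5 h scan. Report adherence from the scan times already on the CRF.
3. Report the same-day 7 h minus 1 h raclopride contrast as supportive only. A constant day offset cancels from it, but it still carries about six hours of clock time and any meal between scans. It also cannot show a fall below baseline: a 1 h rise of 9.5 with no 7 h change would make it significant in over 95% of trials (SD of the difference 5 or 8, alpha 0.0167).
4. State two limitations. One baseline raclopride scan can match only one of the two post-dose scans, so the 7 h contrast with baseline keeps a clock-time difference. Fixed day order also remains mixed with the drug effect.

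**Cost.** No extra scans or subjects. Subjects have one more day of fasting and abstinence, and scheduling is tighter. Counting three raclopride pairs instead of two moves the Bonferroni level from 0.05/2 = 0.025 to 0.05/3 = 0.0167, which takes 7 h power for −6.5% from 99% to 98% (SD 5) or from 73% to 67% (SD 8). For subjects already scanned, record which rule applied.
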